## PROTOCOL

### Background

#### 1. Provide the scientific background, rationale and relevance of this project.

##### INSTRUCTIONS

- This should include a referenced systematic evidenced-based review when possible.
- If this study involves qualitative research explain the major constructs of your study.
- Do not state in this section what you plan to do in this study. This information should be entered later under “What will be done in this protocol?”
- Do not include the bibliography in this section.
- For studies submitted under the Expedited review criteria, this section need not be more than a few paragraphs.
- For those studies where data will be analyzed collaboratively by multiple sites doing a similar study for which there is no common protocol (Collaborative Site Analysis Study) include a description of the common scientific goals/ procedures/data points.
- If this is an update to current templates from Protocol Builder make sure the information throughout the protocol includes the most current information.

##### Answer/Response:

The onset of COVID-19 and the subsequent lockdown imposed on the public brings about a novel set of mental health risks arising from being spatially constricted and the absence of a physically present support network. Prior to the onset of the pandemic, 13.8 million older adults in America lived alone; 28% of the older adult population.

Isolated older adults will have likely seen family connections dramatically reduced due to mobility restrictions and social distancing. This impact has also been felt at Jefferson Area Board of Aging (JABA) facilities across Charlottesville and the wider county areas as the Centers closed in mid-March due to COVID-19. They re-opened in early September, with smaller numbers and trying to make use of outdoor spaces, and large rooms to allow social distancing. JABA estimate that only a third of their service users have returned since reopening in September. It is vital that we understand the impacts of this enforced isolation on mental and social health in order to generate novel measures for mitigating its effects and fostering a higher quality of life in these trying times, and indeed, beyond. Further to this, as we begin to lift state, federal and self-imposed restrictions, we want to understand how to safely bring older adults back into social, outdoor spaces that are optimized to have a beneficial impact on their health and wellbeing. This is a national concern as the Center for Disease Control (CDC) has indicated adults over 65 should engage in developing a care plan as well as providing guidance for coping with stress/anxiety at this time.

One way of allowing increased social activity in a safe environment would be to utilize outdoor green spaces. Research has shown cognitive, social and physiological health benefits of green space interventions in older adults, but what is less understood is how

different activities may deliver positive health benefits to those returning to green social spaces. Adults aged over 45 years have lower levels of distress if they are physically active in greener surroundings, but exposure to green space among those who do no or little activity has no impact on mental health. With social connections severely restricted due to COVID-19, it is important to understand how safe interventions utilizing nature contact/exposure can support mental health and social interactions. This issue is also wider than the current pandemic, with global standards existing for urban spaces to align with the Sustainable Development Goals (SDGs) which include the aim, by 2030, of providing universal access to safe, inclusive and accessible public green spaces, particularly for women and children, older people and people with disabilities. Research on this is limited at present, but evidence suggests exposure to green space can improve sense of belonging and interconnectedness with others in younger cohorts; by logical extension this should follow in other populations, but there is no consensus as to the impacts of nature contact on social connections in older adults.

Our team have developed and piloted a protocol in younger adults (in the UK) to understand how activity type may impact mood. Specifically, we looked at how a 'default activity' in green space (walking in a park) compared to a 'cerebral activity' (citizen science; learning about green space with little to no physical exertion) and 'physical activity' (digging and planting, with little cerebral exertion) to understand green 'dosing'. Using this framework, we seek to understand how different activities might impact older adults in our local community.

## Objectives/Hypothesis

### INSTRUCTIONS:

If this study involves biomedical research clearly state the objectives and hypotheses and clearly define the primary and any secondary outcome measures. If this study involves qualitative research clearly state your research hypothesis or question.

This section should not include information already included in other sections such as background information or information from the procedures section.

### Answer/Response:

Building on pilot work from our team exploring green space activity type, this study aims to focus specifically on older adults in Charlottesville and the surrounding areas. We aim to understand how green space activity type may influence belonging, loneliness and mood and how this may impact on willingness to return to JABA centers. Our research questions are as follows;

1. What types of green space activities have a beneficial impact on loneliness, belonging and mood in seniors who are JABA center members?
2. Does the inclusion of these activities encourage JABA service users to continue participation at their JABA centers?

To investigate these questions, we will utilize 2 study components. The first, titled 'activity sessions' refers to a participant group who will undergo a series of activities (on separate days) including walking, citizen science and planting in order to understand pre- and post-activity wellbeing. The second component, titled 'survey-only', refers to a different participant group who are remotely surveyed on their current wellbeing, experiences during COVID and barriers on returning to JABA. All participants will be JABA service users.

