## Study Design: Biomedical

### 1. Will controls be used?

Answer/Response: Yes

► IF YES, explain the kind of controls to be used.

Answer/Response: There are two controls. First, during the activity sessions, participants will act as their own control, crossing over to take part in each activity. Second, we also will conduct a survey remotely in which participants will respond to questions regarding their current wellbeing. These will be compared to those of the participants who undergo the activity sessions.

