**4. What is your plan for primary variable analysis?**

UVA Study Tracking: HSR210100

Version Date: 03-22-21

Page Number: 6 of 11

Include primary outcome(s)/predictor variable(s), statistical methods/models/tests to be employed, or descriptive summaries as appropriate. If not applicable, please provide explanation.

**Answer/Response:** We will use the following outcome measures across the study.

- Loneliness; measured by the UCLA Loneliness Scale, a 3-item scale that captures feelings of loneliness. (Activities and survey-only)
- Belonging; measured by the General Belonging Scale (GBS), a 12-item scale capturing social acceptance/inclusion and social rejection/exclusion. (Activities and survey-only)
- Acute Mood; pre and post measures of mood will be taken using the UWIST Mood Adjective Checklist (MACL), an acute measure of hedonic tone, stress and arousal. (Activities only)
- Restoration; Psychological restorative qualities of the setting measured by the Perceived Restorativeness Scale, a three point scale determining the restorative quality of activity spaces. (Activities only)
- Physical Activity; In addition to the arousal measure of the MACL, we will use the 10 point scale of the OMNI Perceived Exertion scale, to understand how physically exerted participants feel between activities. To understand baseline physical activity, we use the international physical activity questionnaire (IPAQ) to compare between studies (Activities and survey-only).
- Accelerometer; we will use accelerometers to measure participant movement throughout the activities to correlate with physical activity measures. (Activities only). Specifically, we will look to understand if increased movement, as measured by the accelerometer, correlates with increased feelings of exertion post-activity (across all three activities).

For measures taken in both the activities and survey-only, we will use an independent t-test using condition (activity or survey) to compare. For activities that use pre- and post-assessments, we will make change scores for each and use this in a one-way ANOVA, using activity type (three levels; walking, citizen science, planting) as the grouping variable.

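### Research question 2, on whether the activities encourage continued JABA participation, has no named outcome and no planned analysis, and the data described cannot answer it

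*Combined protocol and SAP*

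**What the plan says.** The Objectives/Hypothesis section gives two research questions. The first concerns which activities benefit loneliness, belonging and mood. The second asks "Does the inclusion of these activities encourage JABA service users to continue participation at their JABA centers". The aim stated above them also covers "how this may impact on willingness to return to JABA centers".

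The same section describes what each group is studied for. The activity group is studied for wellbeing before and after the sessions. The survey-only group is a different set of people "who are remotely surveyed on their current wellbeing, experiences during COVID and barriers on returning to JABA". Under Study Design, question 1, the survey-only group serves as a control in which "participants will respond to questions regarding their current wellbeing", and those answers are compared with the activity group's.

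Statistical Considerations, question 4, opens its list with "We will use the following outcome measures across the study". The bullets are loneliness, belonging, acute mood, restoration, physical activity and accelerometer. For measures shared by the two groups, "we will use an independent t-test using condition (activity or survey) to compare". For pre/post measures, the plan is to form change scores and "use this in a one-way ANOVA, using activity type". A correlation of accelerometer movement with perceived exertion is also planned. Question 5 (secondary analysis) is answered as not applicable. Question 2 mentions barriers to returning as a pilot aim, without a measure or method.

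**The concern.** A stated research question needs an outcome, people in whom it is measured, and an analysis. For the second question the plan names no outcome or analysis. The people described as being asked about returning are not the people who do the activities.

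The protocol form sets this standard itself. Its instructions for the objectives ask the authors to "clearly define the primary and any secondary outcome measures". Its instructions under Statistical Considerations, question 2, require objectives and statistics to match, and objectives that cannot feasibly be analysed to be removed.

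If the plan is followed as written, one of its two questions ends without a planned answer. Any statement about participation would then rest on something chosen after the data were seen. The first research question is not affected.

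**Working it through.** **Step 1. Match the second question against the outcome list** (Statistical Considerations, question 4).

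| Outcome bullet | Concerns return, willingness or attendance? |
|---|---|
| Loneliness | No |
| Belonging | No |
| Acute mood | No |
| Restoration | No |
| Physical activity (exertion scale, activity questionnaire) | No |
| Accelerometer | No |

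Count: 0 of 6.

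**Step 2. Match it against the analyses** (same section).

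| Analysis | Applied to | Addresses the second question? |
|---|---|---|
| Independent t-test | Listed measures shared by both groups | No |
| One-way ANOVA of change scores | Pre/post measures, by activity type | No |
| Accelerometer–exertion correlation | Movement and exertion | No |

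Count: 0 of 3. Question 5 adds nothing.

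**Step 3. Set the two groups side by side** (Objectives/Hypothesis; Study Procedures, question 1).

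| Group | Does the activities | Described as asked about returning |
|---|---|---|
| Activity sessions | Yes | No |
| Survey only | No | Yes (barriers) |

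No group is described as having both. The survey-only answers give context on barriers, but they cannot show whether doing the activities encourages participation. Study Procedures describes no later follow-up of attendance: participation ends after the post-activity survey and payment.

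**Step 4. Reproduce the plan's own sample figure** (Subjects, question 2). 60 × (1 − 0.10) = 54, and 54 / 2 = 27 per group. This agrees with the plan. The plan gives no effect size, standard deviation, error rate or power, so there is no power calculation to reproduce.

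**Step 5. Precision of a simple remedy.** This describes the remedy and does not measure the defect. For a paired mean change, the 95% half-width in standard deviations of the change score is t(0.975, n − 1) / √n.

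- n = 27, everyone expected to complete: 2.056 / 5.196 = 0.396, about ±0.40.
- n = 20, an assumed shortfall: 2.093 / 4.472 = 0.468, about ±0.47.

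The documents give no standard deviation for such an item, so these cannot be converted to scale points.

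**The case against.** Four arguments can be made on the other side.

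*The unseen questionnaires may already ask about returning.* This stands as a limit. Survey content is only briefly described for either group, and Statistical Considerations, question 2, names barriers to returning as an aim of the whole pilot. A reader might infer that activity participants will certainly not be asked about returning. The documents do not support that; they show only that no such question is described or named as an outcome.

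*The t-test and ANOVA are worded as general rules and could cover an unlisted item.* This is partly right. A reader might infer that such an item would necessarily be left unanalysed, and that goes too far. But the rules follow a list that omits any such item. The ANOVA compares activity types with one another, and the t-test compares groups that were not randomized. Neither is identified as the analysis of the second question.

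*It is a pilot with a sample size set by feasibility.* That explains the absence of a power calculation. It does not explain the absence of an outcome for a stated question.

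*The matter need not be settled before sessions begin.* This stands in part. A reader might infer that any solution must be in place before the first session. That is true of a pre/post item, whose baseline cannot be collected later. It may not be true of other designs, such as JABA attendance records. The documents do not say whether such records exist.

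**Conclusion.** The point holds. The second research question has no named outcome and no planned analysis (0 of 6 outcomes, 0 of 3 analyses), and the data described cannot answer it. This rests on the protocol text alone and assumes that the outcome list is meant to be complete, as its opening words indicate.

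The precision of about ±0.40 standard deviations assumes that all 27 expected activity completers supply both a baseline and a later answer. Intervals by attendance status would need an assumed split of those 27 and would add little, so none is offered.

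The point should be addressed, but it does not undermine the study as a whole.

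**What to change.** Name an outcome and an analysis for the second research question in Statistical Considerations, question 4, or delete the question, as the form's own instructions direct.

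One cheap way to keep it:

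- Add, or list if already present, one identical item on how likely the person is to attend their JABA center. Put it in the activity group's first pre-session survey, in every post-session survey and in the mailed survey. Use the last post-session survey completed, so that a missed final session does not lose the participant.
- Record at entry whether the person already attends. The inclusion criteria admit past users, and the Background reports that about a third of users have returned, so continuing and returning would otherwise be mixed.
- Report the within-person change in the activity group with a 95% confidence interval. Describe results by attendance status at entry without formal subgroup inference, and give the survey-only answers as context.
- Reword the question as a descriptive one about stated likelihood of attending.
- State the limits. Stated likelihood is not attendance. The change has no randomization and no concurrent comparator. It may partly reflect being brought back to the center, because the planting session is held there.

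If this item is chosen, it must be in place before the first session.

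The cost is two short questions on surveys already given and one line of analysis. The form becomes slightly longer, and the second question becomes narrower, descriptive and imprecise.

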## Study Design: Biomedical

### 1. Will controls be used?

Answer/Response: Yes

► IF YES, explain the kind of controls to be used.

Answer/Response: There are two controls. First, during the activity sessions, participants will act as their own control, crossing over to take part in each activity. Second, we also will conduct a survey remotely in which participants will respond to questions regarding their current wellbeing. These will be compared to those of the participants who undergo the activity sessions.

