### 2. What is the study design?

Example: case series, case control study, cohort study, randomized control study, single-blind, double-blind, met-analysis, systematic reviews, other. You may also view the IRB-HSR Learning Shot on this topic to help you answer this question.

[https://hrpp.irb.virginia.edu/learningshots/Writing\\_protocol\\_June09/player.html](https://hrpp.irb.virginia.edu/learningshots/Writing_protocol_June09/player.html)

Answer/Response: For the activity sessions, the study is a repeated measures study design. For the survey only group, the study is a single cohort study.

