**2. Describe expected rate of screen failure/ dropouts/withdrawals from all sites.**

**Answer/Response:**

We would expect around 10% attrition, so a final sample of 54 (n = 27 per group) is expected

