## Statistical Considerations

### 1. Is stratification/randomization involved?

Answer/Response: No

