**2. What are the statistical considerations for the protocol?**

The objectives section and the statistical section should correspond, and any objective for which analysis is unfeasible should be deleted. Also, the estimates and non-statistical assumptions of the statistical section should be supported by discussion in the background section.

The answer to this question should include:

- Study Design/Endpoints
- Recap of study objectives and endpoint definitions. An assessment of how study objectives will be assessed by identifying & defining which endpoints will be used to assess each component of the study objectives.
- The study design should include contingencies for early stopping, interim analyses, stratification factors (if applicable), and any characteristics to be incorporated in analyses.
- The power/precision of the study to address the major study endpoint(s), the assumptions involved in the determination of power/precision.
- If statistical hypothesis testing is included then specify the null and alternative hypotheses, the test statistic, and the type I and II error rates
- If precision of an estimate, then provide a definition for precision
- If other, then specify

Answer/Response:

This is a pilot study aimed at ascertaining impacts of outdoor activities on both wellbeing as well as understanding barriers to returning to JABA centers.

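### The plan gives no order for the three crossed-over activities; if all participants follow one order, activity and session number cannot be separated for mood change

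*Combined protocol and SAP*

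**What the plan says.** Under Study Design: Biomedical, question 1, the first of two controls is that "participants will act as their own control, crossing over to take part in each activity". Question 2 adds: "For the activity sessions, the study is a repeated measures study design". Objectives/Hypothesis says that this group "will undergo a series of activities (on separate days) including walking, citizen science and planting".

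Under Statistical Considerations, question 1 ("Is stratification/randomization involved") is answered No, and the scheme is N/A. Study Procedures describes the three sessions one by one but gives no sequence, allocation to sequences or spacing. It places walking and citizen science at a nature preserve and planting at the JABA center.

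For mood, Statistical Considerations, question 4, says that "pre and post measures of mood will be taken". Change scores go into a one-way ANOVA, "using activity type (three levels; walking, citizen science, planting) as the grouping variable". No term for participant, session number or date is named. The secondary analysis is N/A.

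On numbers, Human Participants, question 2, says "a final sample of 54 (n = 27 per group) is expected".

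**The concern.** Acting as one's own control removes stable differences between people. It does not remove the effect of a session being someone's first or third. Mood response could change over sessions through familiarity, growing social contact or season. Pre-to-post change scores cancel drift in the level at which people start each session, but not drift in the size of the response within a session.

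If everyone does the activities in one order, that drift falls entirely on the activity comparison, and no analysis chosen later can take it out. The first research question asks which activity types benefit mood, among other outcomes. Mood is the one outcome that the plan clearly measures before and after each activity. The matter can be settled only before the sessions are run.

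**Working it through.** **Inputs from the plan.** 60 enrolled and about 10% attrition: 60 × (1 − 0.10) = 54, or 27 per group. This reproduces the plan's figure. Before attrition the activity group has 60 / 2 = 30. Each completer contributes three change scores, so there are 27 × 3 = 81 observations.

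**Step 1: can activity and session number be separated?** Take a linear model with 27 participant columns, 2 activity contrasts and 2 session-number contrasts: 31 columns, 81 rows.

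| Order of activities | Rank, of 31 | Rank without session columns |
|---|---|---|
| One common order | 29 | 29 |
| Three balanced (Latin-square) orders | 31 | 29 |
| Six orders | 31 | 29 |

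Under one common order the session columns add nothing, because they repeat the activity columns. This result needs no assumption about drift, variance or correlation.

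**Step 2: size of the bias under one common order.** If the response drifts by d per session, sessions 1, 2 and 3 are shifted by 0, d and 2d. The contrast between the activities held first and last is biased by 2d at any within-person correlation: 0, 0.2, 0.4 and 0.6 SD for d = 0, 0.1, 0.2 and 0.3 SD.

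**Step 3: what the planned test would report.** Assumptions, none of them in the documents: one common order, no true activity difference, change-score SD of 1, a 5% test level, and within-person correlation ρ. Simulated share of studies in which the planned one-way ANOVA declares a difference, at n = 27 (40,000 runs per cell):

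| Drift per session (SD) | ρ = 0 | ρ = 0.3 | ρ = 0.5 |
|---|---|---|---|
| 0 | 5.0% | 1.6% | 0.4% |
| 0.1 | 9.2% | 4.2% | 1.8% |
| 0.2 | 23% | 17% | 12% |
| 0.3 | 48% | 44% | 41% |

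The rates below 5% at zero drift come from a separate feature. The planned ANOVA treats the three sessions of one person as independent, so it is conservative when ρ is positive. With a participant term but still one common order, the rates for ρ of 0.3 to 0.5 are about 5% at zero drift, then 11–14%, 31–42% and 63–77% at drifts of 0.1, 0.2 and 0.3 SD. The better test therefore also picks up drift more readily.

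**Step 4: the design with balanced orders.** With participant, activity and session number in the model, the standard error of an activity contrast is √(2(1 − ρ)/27): √(2 × 0.7/27) = 0.23 SD at ρ = 0.3, 0.27 at ρ = 0 and 0.19 at ρ = 0.5. The session term costs almost nothing: in units of the residual variance, the contrast variance is 0.0741 with or without it for three orders, and 0.0742 against 0.0741 for six.

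**Step 5: what balancing leaves.** Suppose one activity, A, carries over to the next session by c. In the six orders, each of the other two activities follows A in 2 of 6 orders, so c/3 remains in the two contrasts that involve A. In the three cyclic orders, one activity follows A in 2 of 3 orders, so 2c/3 remains in the two contrasts that involve that activity. For c = 0.3 SD this is 0.1 and 0.2 SD.

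**Step 6: should shared session dates also be modelled?** Assume ρ = 0.3, activity means 0, 0.25 and 0.5 SD, and no true date effect. The squared deviations of the means sum to 0.125, so the noncentrality is 27 × 0.125 / 0.7 = 4.82. Power is about 46% with no date term (81 − 31 = 50 error df). Testing activity against dates gives about 35% on 8 df (six groups) and 16% on 2 df (three groups).

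**The case against.** The strongest reply is that harm needs two things that the documents do not establish: a common order, and drift in the response. The activities are listed, not scheduled. A reader might infer from the repeated listing, or from the No on randomisation, that everyone walks first and plants last, and so that the mood comparison is biased as planned. The text does not support that. The No may refer only to the two study components, and it does not rule out counterbalancing without randomisation. This part of the reply stands, so the point is that the plan permits a common order, not that it sets one.

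A reader might also take the missing session term as a defect in itself. With balanced orders, drift does not bias activity contrasts even without that term. It matters mainly if orders vary without balance.

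The rejection rates are a sensitivity range. At a drift of 0.1 SD and ρ = 0.3 the planned test rejects in about 4% of studies, which is not inflated, although the 0.2 SD bias remains. The rates also mix in the effect of ignoring the participant.

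Pilot status is a fair reason for a modest remedy. It does not dispose of the point: the plan says "This is a pilot study aimed at ascertaining impacts of outdoor activities", and neither small size nor pilot status undoes aliasing.

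Finally, the documents do not say how many groups attend or whether participants share dates. A compulsory date term would answer a second hypothetical problem at a possibly heavy cost in power (step 6). That objection is accepted.

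**Conclusion.** The point holds in conditional form and should be fixed before sessions begin. The plan leaves the order unstated. If one common order is used, activity and session number are completely aliased (rank 29 of 31), and this cannot be repaired after data collection. That much follows from the design alone.

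The harm is less certain. The bias is twice the per-session drift in mood response between first and last session, and the drift is unknown. With no drift, or with balanced orders, there is no such bias; the plan assures neither. The claim is limited to mood change.

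**What to change.** 1. **Statistical Considerations, question 1.** State that participants, or the groups in which they already attend, are allocated at random in equal numbers to balanced activity orders: the six possible orders, or three Latin-square orders if only three groups run. Use the sessions already planned where there are several groups. Six orders leave less carry-over in the contrasts.
2. **Statistical Considerations, question 4.** Record session number and date. Analyse mood change with participant, activity and session number in place of the independent-groups one-way ANOVA, and report activity differences with confidence intervals. Treat shared dates as a sensitivity analysis or a stated limitation.
3. **If logistics force one common order.** State the order, keep the participant term, and report activity differences as not separable from session number.
4. **In all cases.** State that carry-over is not removed. Report planting contrasts as activity plus site, since planting is held elsewhere; balancing the order does not change this.

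**Cost.** If several groups already run, the cost is a random list and a rota, with no added sessions. If all 30 would attend as one group, group-sessions rise from 3 to 3 × 3 = 9 with three groups, or 3 × 6 = 18 with six. Those at the preserve rise from 2 to 6 or 12. Where that is not feasible, item 3 applies and adds no sessions.
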